Many practitioners also use fillers with high G prime along the jawline or lateral face to accomplish improving the jowls. This technique, alternatively called "jawline filler, jawline lift", has not received FDA approval. JUVÉDERM VOLUMA® XC injectable gel is currently FDA approved for deep injection in the cheek area to correct age-related volume loss. In practice, we have seen the advent of cheek treatments with Voluma causing noticeable lifting in the jowls and also the nasolabial fold. However, recent experimentation with filler into the mandible lateral to the jowl, sometimes accompanied by injection into the preauricular area by this author has revealed that this area has been underrepresented in filler solutions for jowling.

Protocol Summary

This study is proposed to evaluate the best protocol for achieving improvement in the sagging jawline.

JUVÉDERM VOLUMA™ XC will be injected in each of 16 women with sagging of grades 1-3 using a published jawline evaluation scale (1).

Patients will be randomized 1:1 into 2 groups:

Patient Group 1: JUVÉDERM VOLUMA™ XC 1-2 syringes (each syringe is 1 cc) will be injected bilaterally into the lateral jawline and inferior cheek area (preauricular area) (the latter area will be added if necessary to achieve visual improvement in jowl attenuation). Total syringes used per person will have a range of 1-2)

Patient Group 2: JUVÉDERM VOLUMA™ XC 1-3 syringes (each syringe is 1 cc) will be injected bilaterally into the lateral cheek (zygomatic) area plus JUVÉDERM VOLUMA™ XC 1-2 syringes (each syringe is 1 cc) will be injected into the lateral jawline and inferior cheek area (preauricular area) (the latter area will be added if necessary to achieve visual improvement in jowl attenuation). Total syringes used per person will have a range of 2-5)

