This study proposes to evaluate a new indication for JUVÉDERM VOLUMA™ XC, for which the benefit/risk profile has not been entirely assessed. While the risks of stroke and blindness may be small, the jawline and cheek are highly vascularized areas. Due to limited experience and research associated with dermal filler use in this area, the actual risk is unknown.

Alternatives

Alternatives to treatment include but are not limited to other injectable fillers, surgical implants, and surgery.

Study Purpose and Objectives

Purpose:

The purpose of this clinical investigation is to study the perceived reduction of jowling following a volume replacement treatment using JUVÉDERM VOLUMA™ XC in the jawline or in the jawline and the cheek

Primary Objective:

The primary objective of this study is to see that a clinically relevant jowl improvement can be achieved with hyaluronic acid filler into the jawline and/or cheek (Endpoint #1).

The secondary objective is to determine which of the 2 methods (jowl injection alone or jowl injection with cheek injection) is superior (Endpoint #2).

Study Design

Scope:

The clinical study will include 16 patients at one clinical site.

Duration:

Eligible patients will receive 1 treatment according to the study protocol, and will be followed for a period of 12 months to document safety and efficacy. Patient and/or doctor may choose to have a touchup at 1 month. All subjects will be followed for 12 months from the time of the last injection session.

Patient Selection

Each patient will be evaluated by the Investigator to assess his or her suitability for entry into the study.

- 1. Jowling grade 2-3 by the Lower Face Jawline at Rest Scale (1), by both MD evaluator and patient.
- 2. Female patients must not be pregnant or trying to get pregnant and must have negative urine pregnancy tests before treatment.
- 3. Non-pregnant females ages 35-65 in good general health.
- 4. A study participant must be able to give proper informed consent in writing and be willing to follow the treatment schedule and undertake to carry out all necessary precautions and instructions.
- 5. Able to participate in telemedicine video visits.
- 6. Able to understand the requirements of the study and willing and able to follow all study procedures and attend all study visits, and successfully complete the study.

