- 5. Side Effects and possible adverse reactions will be monitored and documented before and after each treatment. Safety measures will be outlined below.
- 6. Safety exams will be performed prior to and 30 minutes after treatment. These tests include the Snellen Eye Exam, Ocular Motility Exam, and Confrontational Visual Fields Exam. Cranial Nerve evaluations will also be performed prior to and 30 minutes after treatment.
- 7. The patient will be given postoperative instructions.
- 8. Inclusion in the study will require participation in all the follow-up visits.

Return Visits

The subject will have a phone call with the study coordinator at 72 hours.

The subject will return at 2 weeks, 4 weeks, 8 weeks, and either 12 or 16 weeks following the treatment.

The subject will have a live video telemedicine visit at 6 and 12 months after the last injection session.

At all follow up in person visits, photographs will be taken.

Any side effects or adverse events will be noted at each study visit. Any changes in condition, medical history, or medications will be noted.

Safety eye exams will be performed. These tests include the Snellen Eye Exam, Ocular Motility Exam, and Confrontational Visual Fields Exam. Cranial Nerve evaluations will also be performed to further assess vision, oculomotor function, and lower face function.

Patient questionnaire will be completed noting discomfort from the treatment, downtime following treatment, their perception of the results, would they have the treatment performed again in the future if they had the choice, and if they feel they need a touch-up (see below).

The patient or treating physician may request one touchup at one month, with the identical amounts and procedures as the first injection. If this takes place, the patient will have another safety phone visit at 72 hours, another 1-month follow-up visit similar to the first and shall not be eligible for a touch up at the second 1-month visit. The patient shall then have a 3 month visit after the second injection as well as a 6- and 12-month videoconference visit from the second injection. Additional treatment is optional for the patient.

Additional treatment is optional for the patient, but must be agreed upon by both patient and physician that additional improvement may be obtained of the jowl by the treatment.

Safety Assessments

Safety measures include:

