Photographs will remain unretouched. One blinded dermatologist and one unblinded dermatologist will rate the patient's severity of jowling based on the Jawline Rating Scale (JRS) (1) at baseline, the 4-week, 8-week, and 12 or 16-week visits. The patient will also rate their jowling based on the JRS as well as their satisfaction with the procedure.

Analysis of Scientific Soundness of the Protocol

The proposed study has been designed to provide a valid method to analyze the safety and efficacy of facial volume replacement. Measure taken to assure that the study provides valid data are as follows:

- 1. Photographs will be taken under standardized conditions. Photographs will be taken with a VISIA CR, a device made by Canfield Scientific specifically to be utilized for clinical research to provide uniformity in patient photographs.
- 2. Adverse or unanticipated effects that occur during the course of this clinical study will be recorded and carefully analyzed as to their relationship to the treatment.
- 3. Evaluators will review individual photos without knowledge of if they are before or after photos.

Primary Outcome Measure:

The primary outcome is a reduction of 1 or more points of the Jawline Rating Scale (JRS)
 Assessment (on scale of 0 to 4) at baseline versus that at 4 weeks from the last injection (whether initial or touch-up) based on any or all of one blinded dermatologist rating, one unblinded dermatologist rating, and patient rating. (A lower number will mean a better outcome) Time Frame: Baseline to 4 weeks after last injection.

Secondary Outcome Measures

- 1. Reduction of 1 or more points of the Jawline Rating Scale (JRS) Assessment (on scale of 0 to 4) at baseline versus that at 4 weeks from the last injection based on the patients rating while looking in the mirror and at before and after photographs. A lower number will mean a better outcome. Time Frame: 4 weeks from last injection
- 2. Whether group 1 and group 2 has a higher reduction in the Jawline Rating Scale (JRS) (on scale of 0 to 4) at 4 weeks from the lastinjection compared to baseline based on ratings from one blinded dermatologist and one unblinded dermatologist. A lower number will mean a better outcome. Time Frame: 4 weeks from last injection

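### Scoring the primary outcome after the last injection can inflate the Endpoint #1 responder proportion if week-4 non-responders are touched up more often than responders

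*Combined protocol and SAP*

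**What the plan says.** Under Primary Outcome Measure, a responder shows "a reduction of 1 or more points of the Jawline Rating Scale (JRS" from baseline, scored "at 4 weeks from the last injection (whether initial or touch-up" and "based on any or all of one blinded dermatologist rating, one unblinded dermatologist rating, and patient rating". Secondary outcomes 1 to 3 use the same timing from the last injection.

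Under Return Visits: "The patient or treating physician may request one touchup at one month, with the identical amounts and procedures as the first injection". The same section asks the patient, in one questionnaire, how she perceives the result and whether she feels she needs a touch-up. It requires patient and physician to agree that further improvement is possible. A patient who is touched up has a second one-month visit, with no further touch-up allowed there. No JRS score triggers or bars a touch-up.

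The retreatment schedule in Appendix 1 places the blinded evaluation, the patient evaluation, photography and the retreatment decision all at Visit 5 (week 4).

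Under Study Design, Duration: "Eligible patients will receive 1 treatment according to the study protocol", with the touch-up described as optional in the next sentence. Under Scope: "The clinical study will include 16 patients at one clinical site". Both randomized groups receive filler, and there is no untreated group. The objective behind the primary outcome is that "clinically relevant jowl improvement can be achieved with hyaluronic acid filler into the jawline and/or cheek (Endpoint #1".

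**The concern.** Whether a week-4 rating counts depends on a decision made at the visit that produced it. A patient who looks or feels better at week 4 is less likely to want more filler, and her rating stands. A patient who does not is more likely to be injected again and rated again. On a scale where a one-grade drop is a response, the second rating is another chance to be counted as a responder, even if the second injection does nothing. This can happen with equal touch-up rates in the two groups, because it affects the pooled before-and-after proportion and not only the comparison between groups.

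At stake is what the Endpoint #1 proportion means. It can mix the effect of one treatment, the effect of two, and selection on rating error. With 16 patients and no untreated control, that proportion is the main evidence for the primary objective.

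**Working it through.** The plan has no calculation to reproduce. It gives 16 patients but no expected responder rate, threshold, test, rater error or touch-up rate. The check asks how many false responders the scoring rule produces when nothing has truly changed.

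**Inputs**
- From the protocol: 16 patients, response as a drop of at least 1 grade, at most one touch-up (so at most two ratings), and one baseline rating used for both.
- Assumed: one rater, because the protocol gives no rule for combining the three. Each rating is off by one grade with probability e, equally often up and down, with errors independent between visits. Touch-up probability is u for week-4 non-responders and v for week-4 responders. The single-look false-responder rate p is set to 15% or 20%.

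**One look.** Given the baseline error, the chance s that the later rating is at least one grade lower is:
- baseline correct (probability 1 − e): s = e/2
- baseline one grade too high (probability e/2): s = 1 − e/2
- baseline one grade too low (probability e/2): s = 0

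So p = (1 − e)(e/2) + (e/2)(1 − e/2) = e − 0.75e².

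**Last-injection rule.** Given s, the final response probability is s(1 − v) + v·s² + (1 − s)·u·s = s + s(1 − s)(u − v). Averaging over the baseline error gives

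p + (u − v)·D, with D = (e/2)(1 − e/2)².

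**p = 15%.** e = [1 − √(1 − 3 × 0.15)]/1.5 = 0.1723, and D = 0.0861 × 0.9139² = 0.0719.

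**p = 20%.** e = [1 − √(1 − 3 × 0.20)]/1.5 = 0.2450, and D = 0.1225 × 0.8775² = 0.0943.

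| u − v | p = 15%: rate (of 16) | p = 20%: rate (of 16) |
|---|---|---|
| 0 (same as one fixed look) | 15.0% (2.4) | 20.0% (3.2) |
| 0.5 | 18.6% (3.0) | 24.7% (4.0) |
| 1 | 22.2% (3.6) | 29.4% (4.7) |
| −0.25 | 13.2% (2.1) | 17.6% (2.8) |

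At p = 15% the excess is about 0.6 to 1.2 patients of 16. The upper end requires every week-4 non-responder and no responder to be touched up.

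**Which rater.** The touch-up lies with the patient and the treating physician. The patient rates herself at the visit where she helps decide, so for her rating u > v is plausible. The same holds for the unblinded dermatologist if that person is also the treating physician, which is not stated. The blinded dermatologist has no stated role in the decision. If that rater's errors are independent of the others', u − v is about 0 for that rating when there is no true effect.

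**Is the one-treatment result available elsewhere?** Secondary outcome 4 plans the JRS at 4 weeks by all three raters, and does not mention the last injection. It is a score and not a responder proportion, and the Protocol Summary times all visits from the last injection session. It therefore does not clearly give the one-treatment result, although the week-4 rating is scheduled at Visit 5.

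**The case against.** The strongest reply is that the protocol contains no rule sending non-responders back for injection. A reader might infer that an unfavourable week-4 rating leads to a second injection and a favourable one ends the sequence. The text does not say this. A patient who improved from grade 3 to grade 2 is a responder who may still want more; if touched up, she gives up her week-4 rating and may lose her response. The direction depends on u > v. This stands. The agreement that more improvement is possible, and the questionnaire that links perceived result to touch-up, make u > v likely but do not establish it.

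A reader might also treat the two changes from baseline as independent draws, giving p[1 + (1 − p)(u − v)]. At p = 15% and u − v = 1 this is 27.75%, or 4.44 of 16. Both changes subtract the same baseline rating, so they are positively correlated, and the excess over one look is overstated about 1.8-fold (0.1275 against 0.0719).

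Masked photograph order protects against expectation in the evaluators. It does not remove selection on random error, and it does not cover the patient, who under secondary outcome 1 rates with a mirror and with before and after photographs.

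Finally, improvement with an optional touch-up is a legitimate thing to measure, is stated openly, and fits an objective about what can be achieved. A touch-up may also add real benefit. This stands too: the documents do not support calling the primary outcome invalid or replacing it. They do leave real benefit and re-rating inseparable in the reported figure.

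**Conclusion.** The point holds as a conditional one. The timing rule, with ratings and touch-up decision at one visit, can inflate the Endpoint #1 proportion if week-4 non-responders are touched up more often than responders. It bears mainly on the patient's rating, who alone may suffice under the any-or-all wording, and on the unblinded dermatologist's if that rater treats.

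For one rater with no true effect, a 15% single-look rate (2.4 of 16) becomes about 3.0 of 16 at u − v = 0.5 and 3.6 at u − v = 1; a 20% rate becomes about 25% and 29%. It is unchanged if u = v and falls if u < v. These figures rest on assumed rater error and uptake, a symmetric one-grade error and a shared baseline.

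A reader might infer an inflated type I error. No test, null rate or success threshold is stated for Endpoint #1, so the effect is on the reported proportion only.

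**What to change.** Keep the proportion scored from the last injection and label it *with optional touch-up*. Beside it, report:

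- for all 16 patients and for each rater separately, the proportion with a drop of at least 1 point at the week-4 visit after the initial injection, stating that this is rated before any touch-up (Visit 5, already scheduled);
- the number touched up in each group;
- the responder proportion 12 weeks after the last injection, from the data of secondary outcome 6, where no retreatment decision is tied to the rating.

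State also whether the unblinded dermatologist is the treating physician.

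The cost is outcome wording and one extra table, with no new visit or assessment. The small downside is that the one-treatment proportion may be lower than the present one. No touch-up rule is changed.

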- c. There may be discomfort / pain / bruising and complete discussion of side effects potentially resulting from the treatment, including possible stroke, blindness and scarring
- d. Transient edema may occur immediately following the treatment.
- e. Erythema and bruising may occur following treatment and last up two weeks or longer.
- f. A full disclosure and written consent will be provided and signed.
- g. If necessary as deemed by patient and/or physician, a touch up may be performed at the 1-month visit.
- h. Evaluations by phone and/or telemedicine will be performed at 72 hours after treatment, 6 and 12 months.
- I. Patients will complete a safety diary daily via email for 30 days following treatments.

If the patient passes all of the inclusion and exclusion criteria for entry into the study the investigator will obtain signed Informed consent, enroll the patient into the study, and record required data on the appropriate study data form. Pre-treatment photographs will be taken.

Treatment

- 1. Photographs will be taken prior to treatment with the VISIA CR system and Fotofinder and with an iPad. Frontal, 45- and 90-degree angle shots at standard illuminations will be taken.
- 2. Patients will be randomized to 2 groups:

Patient Group 1: JUVÉDERM VOLUMA™ XC 1-2 syringes (each syringe is 1 cc) in will be injected bilaterally into the lateral Jawline/lateral medial or and inferior cheek area (preauricular area) (the latter area will be added if necessary to achieve visual improvement in jowl attenuation). Total syringes used per person will have a range of 1-2.

Patient Group 2: JUVÉDERM VOLUMA™ XC 1-3 syringes (each syringe is 1 cc) will be injected bilaterally into the lateral cheek (zygomatic) area plus JUVÉDERM VOLUMA™ XC 1-2 syringes (each syringe is 1 cc) will be injected into the lateral jawline and inferior cheek area (preauricular area) (the latter area will be added if necessary to achieve visual improvement in jowl attenuation). Total syringes used per person will have a range of 2-5.

Note: Based on preclinical studies and a toxicological risk assessment, subjects will be limited to 20 mL of JUVEDERM VOLUMA™XC per 60 kg (130 lbs) body mass per year. This includes any "Touch-up Volume"

3. During treatment cold air will be directed toward the injection sites to reduce discomfort.

- 4. Any complications will be noted at each visit and the patient will complete a diary via email or text every day.

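### The primary outcome accepts any or all of three ratings without giving the blinded one priority, so the patient's own rating can make a responder by itself

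*Combined protocol and SAP*

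**What the plan says.** The section Primary Outcome Measure defines the outcome as a reduction of 1 or more JRS points from baseline to 4 weeks after the last injection, "based on any or all of one blinded dermatologist rating, one unblinded dermatologist rating, and patient rating". The available text does not say how many ratings must improve, how disagreement is settled, or that the blinded rating leads.

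Other places bear on this:

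- **Objective.** The primary objective is "to see that a clinically relevant jowl improvement can be achieved". The stated purpose just above it is "to study the perceived reduction of jowling following a volume replacement treatment".
- **Treatment.** Under Protocol Summary, the filler "will be injected in each of 16 women". The two groups differ in injection sites; neither is untreated or sham-treated.
- **Masking.** Analysis of Scientific Soundness of the Protocol, item 3, states: "Evaluators will review individual photos without knowledge of if they are before or after photos".
- **Patient rating.** Secondary outcome 1 takes the same 1-point reduction, "based on the patients rating while looking in the mirror and at before and after photographs".
- **Other outcomes.** Secondary outcomes 2 and 3 compare the groups, on the two dermatologists' ratings and on the patient's rating respectively. Secondary outcome 4 lists the 4-week JRS by all three raters. No listed outcome is a response rate on the blinded rating alone.

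**The concern.** The plan collects one rating meant to be protected from knowledge of treatment, then lets a rating without that protection decide the primary outcome alone. The patient knows she was injected, and she rates herself in the mirror and beside before and after photographs. Item 3 cannot apply to a rating made that way.

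The primary objective is a before-and-after claim in patients who are all treated. A hopeful self-rating is not balanced by equally hopeful self-ratings in an untreated group. As written, the plan can report a favourable primary outcome on patient ratings alone, whatever the blinded dermatologist records. The available text gives no success threshold that would limit this.

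**Working it through.** **No figure to reproduce.** The text gives no expected response rate, success threshold, significance level, sample-size derivation or rater-agreement figure.

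**Step 1: bounds that need no assumed rates.** Inputs are n = 16 (Protocol Summary and Scope) and three ratings per patient (Primary Outcome Measure). The response is counted per patient, the natural reading of a reduction of 1 or more points. Let B, U and P be the sets of patients with a fall of at least 1 point according to the blinded dermatologist, the unblinded dermatologist and the patient, and let B contain k patients.

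- *Any*: the number in B ∪ U ∪ P lies between k and 16.
- *All*: the number in B ∩ U ∩ P lies between 0 and k.
- *Any*, without the unblinded dermatologist: the number in B ∪ P still lies between k and 16, so patient ratings alone can reach the upper bound.

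Example with k = 5: the blinded rate is 5/16 = 31%, *any* can report 5 to 16 responders, and *all* 0 to 5.

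**Step 2: illustration under assumed rates.** Suppose there is no true change. Each dermatologist records a 1-point fall by chance in 10% of patients, and the patient, with some expectation of benefit, in 20% or 30%. These rates are assumptions.

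- Independent raters: *any* = 1 − (1 − p1)(1 − p2)(1 − p3).
  - Patient 20%: 1 − 0.9 × 0.9 × 0.8 = 0.352.
  - Patient 30%: 1 − 0.9 × 0.9 × 0.7 = 0.433.
- Correlated raters: one shared normal factor with common latent correlation r. This is more plausible, since all three grade the same face.
- Blinded dermatologist and patient only, independent: 1 − 0.9 × 0.8 = 0.280 and 1 − 0.9 × 0.7 = 0.370.

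| Chance of counting as a responder | r = 0 | r = 0.6 | r = 0.8 | r = 0.95 |
|---|---|---|---|---|
| *Any* of three, patient 20% | 35% | 27% | 24% | 21% |
| *Any* of three, patient 30% | 43% | 35% | 32% | 30% |
| Blinded or patient, patient 20% | 28% | 24% | 22% | 20% |
| Blinded or patient, patient 30% | 37% | 33% | 31% | 30% |
| Blinded alone | 10% | 10% | 10% | 10% |

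At r = 0.8, *any* of three gives 16 × 0.236 = 3.8 to 16 × 0.317 = 5.1 expected responders, against 16 × 0.10 = 1.6 for the blinded rating. *Any* can never fall below its largest component, so the high-correlation columns largely return the patient rate that was put in. They show that close agreement between raters does not remove the effect; they do not estimate its size in this trial.

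**Step 3: is the blinded rating masked to before and after?** Three places do not yet agree.

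- Item 3 has individual photographs rated without knowledge of order.
- The Blinded Physician Assessment form has fields in its header for baseline, the week, and first or second injection. It also asks for a comparison of the pre-injection photograph with the current one. A rater completing it as laid out could know the time point.
- Both schedules in Appendix 1 put the baseline Blinded Evaluation at Visit 1 and the first Photography at Visit 2. Pre-Procedure Evaluation does say that "Pre-treatment photographs will be taken", but that does not settle which material is used for the baseline grade.

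**Step 4: precision of a single-rater proportion.** The exact (Clopper-Pearson) 95% limits for x of 16 are the 2.5% point of Beta(x, 17 − x) and the 97.5% point of Beta(x + 1, 16 − x).

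- 5/16: 11% to 59%
- 10/16: 35% to 85%
- 13/16: 54% to 96%

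**The case against.** The study's purpose is worded as perceived reduction, so a patient rating inside the primary outcome is a defensible choice. All three ratings are collected, and secondary outcomes 1 and 4 bring out the patient's response and each rater's 4-week grade. The result is descriptive in 16 patients. Co-primary outcomes or a stated combination rule would also end the ambiguity.

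Much of this stands. Rater-specific results can be recovered, and other explicit rules are possible. But perception already has its own endpoint in secondary outcome 1, and recoverable data do not settle which result is primary.

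A reader might infer four stronger points that the documents do not support:

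- *The rule is undefined.* In ordinary use, any or all means one or more, which is a rule. The main trouble is what that rule permits.
- *The unblinded dermatologist's rating is equally exposed.* Item 3 speaks of evaluators generally, and the text does not say what this rater is unblinded to. The point rests on the patient's rating alone.
- *The group comparison is compromised.* Secondary outcomes 2 and 3 have their own definitions and do not use this rule.
- *The primary rate will be inflated by a known amount.* Only the bounds in step 1 follow without assumed rates.

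**Conclusion.** The defect holds and should be corrected before the ratings are analysed. The stated rule lets a rating by a patient who knows she was treated produce the primary result against the blinded dermatologist's finding, in a design with no untreated arm. Its possible size is k to 16 responders under *any* and 0 to k under *all*, where k is the blinded count. This assumes per-patient counting and the text available for review. Under the assumed rates above, a 10% blinded rate becomes roughly 21% to 43%, as illustration only.

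Naming the blinded rater is necessary but not sufficient. Unless the form and schedule are brought into line with item 3, that rating may itself not be masked to before and after.

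**What to change.** 1. Delete *any or all of*. Define the primary outcome as the proportion of patients with a fall of at least 1 JRS point, from baseline to 4 weeks after the last injection, on the blinded dermatologist's rating alone. Report it with an exact 95% confidence interval.
2. Add the unblinded dermatologist's response rate as a separate secondary outcome. Keep the patient's as secondary outcome 1.
3. Reconcile Appendix 1 and the Blinded Physician Assessment form with item 3. Have the blinded dermatologist grade the pre-treatment photograph and the photograph from 4 weeks after the last injection individually, in hidden order. Remove the visit and injection fields from the form the rater sees for the JRS grade. Put the before-and-after comparison question on a separate form, completed afterwards.

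Requiring all three raters would also be unambiguous and could not exceed the blinded rate, but it would let the patient's rating overrule a blinded response.

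The cost is wording, one secondary outcome line, and small form and schedule edits, with no new visit, rater or photograph. The headline rate will probably be lower than under *any*, and the patient's view becomes secondary only. The change does not say what proportion would count as clinically relevant; that remains for the sponsor to state.
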